### **8.1.1 Criteria to Resume Treatment**

Participants will be permitted to resume study treatment at the same dose level(s) following resolution of the AE to  $\leq$  Grade 1 or to baseline with the exception of participants who meet criteria for permanent discontinuation of study treatment (see [Section 8.1](#)):

- For participants receiving two cycles of combination treatment, the first dose of BMS-986277 in Cycle 2 may be delayed by up to 7 days (up to study Day 36) in the case of persistence of AEs from the preceding cycle as listed above. After this time, nivolumab monotherapy may be continued.
- Nivolumab dosing may be delayed by up to 6 weeks; the participant should restart treatment on the next regularly scheduled nivolumab dosing visit. Doses are not to be replaced only delayed. If nivolumab treatment is delayed  $> 6$  weeks the participant must permanently discontinue study treatment except as specified in Section 8.1.

Tumor assessments for all participants should continue according to the schedule of assessments ([Section 2](#)) **even if dosing is delayed**.

Participants may resume treatment with study treatment when the drug-related AE(s) resolve to Grade  $\leq 1$  or baseline value, with the following exceptions:

- Participants may resume treatment in the presence of Grade 2 fatigue.
- Participants who have not experienced a Grade 3 drug-related skin AE may resume treatment in the presence of Grade 2 skin toxicity.
- For participants with Grade 2 AST, ALT and/or Total Bilirubin Abnormalities, dosing may resume when laboratory values return to baseline and management with corticosteroids, if needed, is complete.
- Drug-related pulmonary toxicity, diarrhea or colitis must have resolved to baseline before treatment is resumed. Participants with persistent Grade 1 pneumonitis after completion of a steroid taper over at least 1 month may be eligible for retreatment if discussed with and approved by BMS Medical Monitor (or designee).

Participants with drug-related endocrinopathies adequately controlled with only physiologic hormone replacement may resume treatment after consultation with the BMS Medical Monitor (or designee). Adrenal insufficiency (Grade 4) requires discontinuation regardless of control with hormone replacement.

### **8.1.2 Treatment Beyond Disease Progression with Nivolumab in Parts 2 and 3**

Accumulating evidence indicates a minority of participants treated with immunotherapy may derive clinical benefit despite initial evidence of progressive disease (PD).

Participants will be permitted to continue nivolumab treatment beyond initial PD defined by RECIST 1.1 or PCWG3 for prostate cancer, as assessed by the investigator, up to a maximum of 2 years from date of first dose of study treatment as long as they meet the following criteria:

- Investigator-assessed clinical benefit
- Tolerance of study treatment
- Stable performance status
- Treatment beyond progression will not delay an imminent intervention to prevent serious complications of disease progression (eg, CNS metastases)
- Participant provides written informed consent prior to receiving additional nivolumab treatment. All other elements of the main consent including description of reasonably foreseeable risks or discomforts, or other alternative treatment options will still apply.
- For participants in Part 3 Cohort 3, progression must be subsequent to start of nivolumab treatment

The assessment of clinical benefit should be balanced by clinical judgment as to whether the participant is clinically deteriorating and unlikely to receive any benefit from continued treatment with nivolumab. If the investigator feels that the participant continues to achieve clinical benefit by continuing nivolumab treatment, the participant should remain on the trial and continue to receive monitoring according to the Schedule of Activities (see [Section 2](#)). All decisions to continue treatment beyond initial progression must be approved by the BMS Medical Monitor (or designee), and an assessment of the risk/benefit of continuing with study therapy must be documented in the study records (see [Appendix 2](#)).

Participants must be re-consented with an ICF addendum or similar document to continue treatment beyond progression. Treatment beyond progression will require continued tumor assessments and scans should continue to be submitted to the imaging core laboratory.

For the participants who continue nivolumab therapy beyond progression, participants will continue to receive monitoring according to the on-treatment assessments in [Section 2](#) and radiographic assessment, per [Section 9.1.1](#) to determine whether there has been continued disease progression or not.

Further progression is defined as an additional 10% increase in tumor burden with a minimum 5 mm absolute increase from time of initial PD. This includes an increase in the sum of diameters of all target lesions and/or the diameters of new measurable lesions compared to the time of initial PD. Nivolumab treatment should be discontinued permanently upon documentation of further progression.

New lesions are considered measureable at the time of initial progression if the longest diameter is at least 10 mm (except for pathological lymph nodes which must have a short axis of at least 15 mm). Any new lesion considered non-measurable at the time of initial progression may become measureable and therefore included in the tumor burden if the longest diameter increases to at least 10 mm (except for pathological lymph nodes which must have a short axis of at least 15 mm). In situations where the relative increase in total tumor burden by 10% is solely due to

inclusion of new lesions which become measurable, these new lesions must demonstrate an absolute increase of at least 5 mm.

### **8.1.3 Post Study Treatment Follow-up**

In this study, OS is an exploratory endpoint of the study. Post study follow-up is of critical importance and is essential to preserving participant safety and the integrity of the study. Participants who discontinue study treatment must continue to be followed for collection of outcome and/or survival follow-up data as required and in line with [Section 5](#) until death, completion of the long-term general health status ([Section 5.1.7.1](#)), or the conclusion of the study.

BMS may request that survival data be collected on all treated participants outside of the protocol defined window (see [Section 2](#)). At the time of this request, each participant will be contacted to determine their survival status unless the participant has withdrawn consent for all contacts or is lost to follow-up.

Participants who discontinue study treatment will continue to be followed for at least 1 year in the long-term general health status follow-up ([Section 5.1.7.1](#)).

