  - Cohort 3 will include participants with high CD8 TILs CD8 ≥ 20% who will receive treatment with BMS-986277 (up to 2 cycles of 28 days each) at the dose level recommended for BMS-986277 monotherapy in Part 1. Following 2 cycles of BMS-986277 monotherapy, participants may receive nivolumab treatment (480 mg Q4W) for up to 26 cycles of 28 days each if eligibility criteria continue to be met (see [Sections 6.1](#) and [6.2](#)). Participants whose disease progresses prior to receiving Cycle 2 of BMS-986277 may also receive nivolumab treatment if eligibility criteria continue to be met (see [Sections 6.1](#) and [6.2](#)), skipping any remaining monotherapy visits and proceeding directly to Cycle 3, optional nivolumab treatment. See [Section 5.1.3](#) and [Table 2-5](#). For

- participants whose disease is responding (complete or partial) per RECIST v1.1 or PCWG3 at the 8 week scan, treatment must be discussed and agreed upon with the Medical Monitor (or designee) prior to the start of the optional subsequent nivolumab treatment.
- Participants treated with BMS-986277 monotherapy only (Part 1 and Part 3 Cohort 3) will be treated until disease progression, unacceptable toxicity, withdrawal of consent, or the completion of the 2 cycles of BMS-986277, whichever occurs first. However, participants treated with nivolumab sequentially in Cohort 3 Part 3 will follow the criteria for BMS-986277 and nivolumab treatment.
  - Participants treated with BMS-986277 and nivolumab (Part 2 and Part 3 Cohorts 1-3) will be treated until disease progression, unacceptable toxicity, withdrawal of consent, or the completion of the 26 cycles of nivolumab, whichever occurs first.
  - All participants treated with BMS-986277 monotherapy only (Part 1 and Part 3 Cohort 3) will attend at least two safety follow-up visits (see [Table 2-6](#) and [Sections 5.1.5](#) and [5.1.6](#)), and be monitored during long-term follow-up (ie, survival, overall health, and response) for up to 3 years post first dose of study medication (specific durations are specified in [Sections 5.1.7.1](#) and [5.1.7.2](#)).

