  - All participants treated with BMS-986277 and nivolumab (Part 2 and Part 3 Cohorts 1-3) will attend at least three safety follow-up visits (see [Table 2-7](#) and [Sections 5.1.5](#) and [5.1.6](#)), and be monitored during long-term follow-up (ie, survival, overall health, and response) for up to 3 years post first dose of study medication (specific durations are specified in [Sections 5.1.7.1](#) and [5.1.7.2](#)).

For all participants, tumor assessments should occur as outlined in [Section 2](#) (Schedule of Activities). Images will be submitted to an imaging core lab for all participants and may be reviewed by Blinded Independent Central Review (BICR) at any time during the study. Treatment decisions will be assessed by the investigator per study design using RECIST v1.1 or PCWG3 criteria.

Clinical progression/deterioration of disease will be monitored throughout the study for all participants.

[figure not shown]
Safety assessments (AEs, PE, vital signs, laboratory safety tests, 12-lead ECGs, cytokine release monitoring, and ECOG performance status) will be evaluated throughout the study treatment and required follow-up visits. Viral shedding and ADA will be monitored at the 30 and 60 day follow-up visits. Additional monitoring may occur at subsequent follow-up visits as clinically indicated in [Table 2-6](#) (participants treated with BMS-986277 monotherapy only [Part 1 and Part 3 Cohort 3]) and [Table 2-7](#) (participants treated with BMS-986277 and nivolumab [Part 2 and Part 3 Cohorts 1-3]). AE monitoring will be continued throughout the study treatment and required follow-up visits as indicated in [Table 2-6](#) and [Table 2-7](#). Concomitant medications will be collected throughout the study treatment (14 days prior to C1D1) and required follow-up visits as indicated in [Table 2-6](#) and [Table 2-7](#).

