#### **5.1.7.1 Long-Term General Health Status Follow-up**

After completion of the safety follow-up visits and in parallel to survival and response follow-up, all treated participants will enter long-term general health status follow-up. During either a visit or phone contact, general health status will be collected and must include specific assessment of new infections, malignancy, and serious adverse events that are hematologic, immunologic, or neurologic. Participation on other clinical trials and subsequent anti-cancer therapy (eg, chemotherapy exposure) will be collected as part of survival follow-up. Participants will be followed approximately every 3 months ( $\pm$  14 days) from the last required safety follow-up visit, for a minimum of 1 year from the last dose of BMS-986277 treatment.

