#### **5.1.7.2 Survival Follow-up**

After completion of the safety follow-up visits and in parallel to long-term general health and response follow-up, all treated participants will enter survival follow-up. Participants will be followed approximately every 3 months ( $\pm$  14 days) from the last required safety follow-up visit, until death, loss to follow-up, withdrawal of consent, or conclusion of the study, whichever occurs first. The duration of survival follow-up is at least 3 years from the first dose of study treatment, although a longer follow-up period could be considered in selected cases if an efficacy signal is apparent. When contacted for survival by visit or phone contact, survival status and subsequent anti-cancer therapy including treatment on other clinical trials will be collected. BMS may request that survival data be collected on all treated participants outside of the 3 month specified window. At the time of this request, each participant will be contacted to determine their survival status unless the participant has withdrawn consent for all contact.

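### Protocol 8.1.3 lets survival follow-up stop when the 1-year health-status follow-up is complete, which contradicts the rule of at least 3 years in 5.1.7.2

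*Protocol*

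**What the plan says.** Protocol Section 5.1.7.2 is the dedicated survival rule. All treated participants are contacted about every 3 months "until death, loss to follow-up, withdrawal of consent, or conclusion of the study, whichever occurs first". It adds: "The duration of survival follow-up is at least 3 years from the first dose of study treatment", with longer follow-up possible if an efficacy signal appears.

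Section 5.1.7.1 is a separate activity, general health status, which runs in parallel "for a minimum of 1 year from the last dose of BMS-986277 treatment".

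Section 8.1.3 covers participants who stop study treatment. It requires "collection of outcome and/or survival follow-up data as required and in line with" Section 5, but the same sentence sets the end as "until death, completion of the long-term general health status" (citing 5.1.7.1) or the conclusion of the study. It later repeats: "Participants who discontinue study treatment will continue to be followed for at least 1 year in the long-term general health status follow-up".

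Section 5.1 (On Treatment) says participants will "be monitored during long-term follow-up (ie, survival, overall health, and response) for up to 3 years post first dose of study medication", and refers to 5.1.7.1 and 5.1.7.2 for the specific durations.

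Section 8.1.3 calls OS exploratory. Section 10.3.1 plans median OS and OS rates at 3, 6, 9 and 12 months. SAP Section 8.5 adds a Kaplan-Meier plot of OS.

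**The concern.** Section 8.1.3 is the section a site would consult when a participant comes off treatment, and it attaches the end of the health-status activity to survival data. The two activities have different clocks and lengths: at least 1 year from the last virus dose against at least 3 years from first dose. BMS-986277 is limited to two cycles, so the shorter clock starts early, while nivolumab can continue for up to 26 cycles.

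If sites applied 8.1.3 as written, a participant who stopped nivolumab early could leave survival follow-up soon after the first year, while one still on nivolumab would stay under observation. Nivolumab normally stops at progression, so whether a late death is observed would depend on prognosis. Kaplan-Meier estimation assumes that it does not. What is at stake is the late part of the OS curve, which is where a durable survival signal, the reason 5.1.7.2 gives for longer follow-up, would have to be seen. Survival data not collected at the time may not be recoverable later.

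**Working it through.** No planned figure is available to reproduce, because the documents give no survival assumption. The check is calendar arithmetic from the dosing schedule, then an illustration of the bias.

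**Inputs.** Last planned BMS-986277 dose: Cycle 2 Day 5 (Protocol Tables 7.1.3-1, 7.1.4-1, 7.1.5-1, 7.1.6-1). Cycle 1 lasts 42 days in Part 1 and 28 days in Parts 2 and 3. Health-status minimum: 1 year from that dose (5.1.7.1). Last safety visit after nivolumab: about 100 days after last dose (5.1.5), with survival status also collected at the safety visits (Table 2-7). Conversion: 30.4375 days per month (SAP 9.1).

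**Earliest end of health-status follow-up** = (days from first dose to last BMS-986277 dose + 365) / 30.4375.

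| Case | Days to last dose | Months from first dose |
|---|---|---|
| Parts 2-3, two cycles | 28 + 4 = 32 | 397 / 30.4375 = 13.04 |
| Parts 2-3, two cycles, 7-day Cycle 2 delay and full 7-day dosing window | 28 + 7 + 7 = 42 | 407 / 30.4375 = 13.37 |
| Parts 2-3, one cycle | 4 | 369 / 30.4375 = 12.12 |
| Part 1, two cycles | 42 + 4 = 46 | 411 / 30.4375 = 13.50 |
| Part 1, one cycle | 18 | 383 / 30.4375 = 12.58 |
| A single dose | 0 | 365 / 30.4375 = 11.99 |

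Under 5.1.7.2 the floor is 3 × 365.25 / 30.4375 = 36.0 months. The literal 8.1.3 stop could therefore lose up to 36.0 − 13.0 = 23 months per participant (22.5 in Part 1).

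These are earliest ends. If health-status follow-up is taken as complete at the first 3-monthly contact on or after 1 year, it ends at month 15.5 in Part 1 (two cycles), and between about month 13.2 and 15.9 for combination participants who stop nivolumab by Cycle 11.

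**Who would still be observed.** A last nivolumab dose at Cycle 13 Day 15 (day 350, month 11.5) is covered by safety visits to 450 / 30.4375 = month 14.8. A last dose at Cycle 26 Day 15 (day 714, month 23.5) is covered to 814 / 30.4375 = month 26.7. So after about month 13 the risk set in the nivolumab-treated parts would be mainly participants on nivolumab or within about 100 days of it. Part 1 gives no nivolumab: there everyone stops on the same clock, which is truncation and not selection.

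**Illustration of the bias (assumptions not from the documents).** Simulated progression and post-progression times, 400,000 participants per scenario. Participants progressing before month 13 are followed to month 13.1 or to progression + 3.3 months, whichever is later; the others to progression + 3.3 months, at most month 36. Pre-progression time is 30% to 50% of mean survival. A shared gamma frailty (shape 1.5), which correlates the two times, is either included or removed. Stopping nivolumab is equated with progression.

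| True median OS | 24-month OS, frailty: true vs read | 24-month OS, no frailty: true vs read | Median read |
|---|---|---|---|
| 9 months | 21% vs 31-34% | 6-8% vs 14% | 9.0 (unchanged) |
| 12 months | 28% vs 40-43% | 15-17% vs 28% | 12.0 (unchanged) |
| 18 months | about 40% vs 54-56% | 35% vs 50-52% | about 24-25 without frailty; with frailty about 36 or not reached |

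The 3-, 6-, 9- and 12-month rates are identical under both stopping rules in every scenario. The direction of the late bias does not depend on the frailty, but its size does.

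**The case against.** The strongest defence is that no site following the schedule would stop early. Tables 2-6 and 2-7 list health status and survival in separate rows, the survival row pointing to 5.1.7.2. Section 5.1.7 says the two run in parallel, each for its own duration. Section 8.1.3 itself says in line with Section 5. The sponsor may request survival status on all treated participants at any time, and Sections 8.2 and 8.3 allow public vital-status sources. This makes the literal reading less likely in practice, and it stands as mitigation. It does not remove the conflict: the same sentence of 8.1.3 names 5.1.7.1, not 5.1.7.2, as the end point, and a sponsor request is discretionary and does not replace a stop rule.

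Some stronger readings are tempting, and the documents do not support them:

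- *Three rival end points.* The wording "for up to 3 years post first dose of study medication" in Section 5.1 is a ceiling that meets the floor of 5.1.7.2 at 3 years, and its sentence defers to 5.1.7.1 and 5.1.7.2. The material conflict is 8.1.3 against 5.1.7.2.
- *A fixed end at month 13, or 1 year after discontinuation.* One year is a minimum and runs from the last BMS-986277 dose. If it ran from discontinuation, a last nivolumab dose at month 5.1 would give follow-up to month 17.0.
- *Only participants still on nivolumab remain at risk.* The 100-day visits keep recent discontinuers under observation, and Section 8.1.2 allows some treatment beyond progression.

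**Conclusion.** The contradiction is in the text, and 8.1.3 is wrong as written. Taken literally, it permits survival follow-up to end about 23 months before the floor in 5.1.7.2. In the nivolumab-treated parts it would make late censoring depend on prognosis, so that the OS tail, and any median beyond about month 13, would tend to be biased upward. In Part 1 it would only shorten the curve; the same clock applies to Cohort 3 participants who never take the optional nivolumab.

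The impact is limited. OS is exploratory, the planned 3- to 12-month rates fall at or before the earliest stop (11.99 to 13.5 months), and medians below about 13 months are essentially unaffected. A reader might take the 24-month figures above as the expected bias. They are not: the plan lists no 24-month rate, the progression and survival assumptions are not in the documents, and the figures suppose that every site applies 8.1.3 literally with no sponsor request for survival status. They support the direction and show that the size could matter. The month-13 figure rests on the planned schedule, two cycles and the minimum health-status duration.

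**What to change.** In Protocol Section 8.1.3, state that survival data are collected until survival follow-up ends under Section 5.1.7.2, and limit completion of Section 5.1.7.1 to the health-status data. As a minor alignment, reword the two Section 5.1 statements of up to 3 years so that they agree with the at-least-3-years rule in 5.1.7.2, to which they already refer.

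The cost is wording in two sections. The 3-monthly survival contacts are already scheduled in 5.1.7.2 and Tables 2-6 and 2-7, so no visits, procedures or analyses are added.

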## **8.2 Discontinuation from the Study**

Participants who request to discontinue study treatment will remain in the study and must continue to be followed for protocol specified follow-up procedures. The only exception to this is when a participant specifically withdraws consent for any further contact with him/her or persons previously authorized by participant to provide this information.

- Participants should notify the investigator of the decision to withdraw consent from future follow-up **in writing**, whenever possible.
- The withdrawal of consent should be explained in detail in the medical records by the investigator, as to whether the withdrawal is from further treatment with study treatment only or also from study procedures and/or post treatment study follow-up, and entered on the appropriate CRF page.
- In the event that vital status (whether the participant is alive or dead) is being measured, publicly available information should be used to determine vital status only as appropriately directed in accordance with local law.
- If the participant withdraws consent for disclosure of future information, the sponsor may retain and continue to use any data collected before such a withdrawal of consent.

## **8.3 Lost to Follow-Up**

- All reasonable efforts must be made to locate participants to determine and report their ongoing status. This includes follow-up with persons authorized by the participant.
- Lost to follow-up is defined by the inability to reach the participant after a minimum of **three** documented phone calls, faxes, or emails as well as lack of response by participant to one registered mail letter. All attempts should be documented in the participant's medical records.
- If it is determined that the participant has died, the site will use permissible local methods to obtain date and cause of death.

- If investigator's use of third-party representative to assist in the follow-up portion of the study has been included in the participant's informed consent, then the investigator may use a Sponsor retained third-party representative to assist site staff with obtaining participant's contact information or other public vital status data necessary to complete the follow-up portion of the study.
- The site staff and representative will consult publicly available sources, such as public health registries and databases, in order to obtain updated contact information.
- If after all attempts, the participant remains lost to follow-up, then the last known alive date as determined by the investigator should be reported and documented in the participant's medical records.

